8.4.2. Supportive Secondary Endpoints

Treatment Failure-free Survival per Investigator Assessment

Treatment failure-free survival per investigator assessment is defined as the time from randomization to the first occurrence of documented radiographic disease progression per RECIST 1.1 as assessed by the investigator or unacceptable toxicity leading to treatment discontinuation as assessed by the investigator (regardless if a study drug-related AE meets protocol guidance for treatment discontinuation or not); or death (due to any cause). Treatment failure-free survival per investigator assessment will be analyzed using the same methodology as for the TFFS per BICR.

Progression-free Survival per Investigator Assessment

Progression-free survival per investigator assessment is defined according to the same criteria and will be analyzed using the same methodology as for the PFS per BICR.

One more censoring rule will be implemented as a part of sensitivity analyses: considering symptomatic deterioration as tumor progression. In this situation the earliest date of PD per RECIST 1.1 criteria, symptomatic deterioration or death will be assigned as an event date.

Overall Response Rate and Duration of Response

Overall response rate (ORR) is defined as the number of patients who achieve a best overall response (BOR) of CR or partial response (PR) divided by the total number of patients randomized to each treatment arm. Best overall response is determined from a sequence of responses assessed. Two objective status determinations of CR before progression are required for a best response of CR. Two determinations of PR or better before progression, but not qualifying for a CR, are required for a best response of PR. The second objective response is required to be ≥ 28 days after the initial response. Tumor assessments performed after initiation of new anticancer treatment (systemic therapy) will be excluded from evaluating the BOR. Patients who do not have any post baseline tumor response assessments are considered nonresponders and are included in the denominator when calculating the response rate.

Disease control rate (DCR) is defined as the number of patients who achieve a BOR of CR, PR or stable disease (SD) lasting 16 or more weeks divided by the total number of patients randomized to each treatment arm.

The ORR and DCR, with 95% CI, will be summarized for each treatment arm. Overall response rate and DCR will be compared between Arm A and Arm B using a Cochran-Mantel-Haenszel (CMH) test stratified by the randomization strata. The ORR and DCR according to both BICR and investigator-assessed BOR will be evaluated.

Maximum change in tumor size is defined as the ratio of best postbaseline tumor size over that of baseline. The maximum reduction from baseline in the sum of target lesions (based on investigator assessment) will be presented per patient in a waterfall plot.

Duration of response (DOR) is defined as the time from the date that measurement criteria for CR or PR (whichever is first recorded) are first met until the first date that disease is recurrent or documented disease progression is observed, per RECIST 1.1 criteria, or the date of death from any cause in the absence of documented disease progression or recurrence. The DOR according to both BICR and investigator-assessed BOR will be evaluated. The DOR will be analyzed for patients who achieve a BOR of CR or PR.

Duration of response will be compared between treatment arms using a stratified logrank test, stratified by the randomization strata. The corresponding HR between treatment arms will be estimated using a stratified Cox regression model (Cox 1972), stratified by the randomization strata. Survival curves, the median and rates at various time points with 95% CI, for each treatment arm will be estimated using the Kaplan-Meier method (Kaplan and Meier 1958).

Overall Survival

Overall survival (OS) is defined as the time from randomization until death from any cause. If the patient is alive or lost to follow-up at the time of data analysis, OS data will be censored on the last date the patient is known to be alive.

The study is not powered for OS but will continue to approximately 125 OS events or until a maximum of 6 years from the first patient visit, whichever comes first. If the true OS HR is 0.7, 125 OS events will provide approximately 98% probability that the observed OS HR would be less than 1.0, indicating no OS detriment associated with the selpercatinib treatment. A HR of 0.7 translates into a 42.9% relative and 30 months absolute increase in median OS (if assuming a median OS of 70 months for cabozantinib/vandetanib and 100 months for selpercatinib).

Overall survival will be compared between treatment arms using a stratified logrank test, stratified by the randomization strata. The corresponding HR between treatment arms will be estimated using a stratified Cox regression model (Cox 1972), stratified by the randomization strata. Overall survival curves, the median and OS rates at various time points with 95% CI, for each treatment arm will be estimated using the Kaplan-Meier method (Kaplan and Meier 1958).

Multiple sensitivity analyses for the OS will be conducted as defined below:

- using an unstratified logrank test and an unstratified Cox regression model
- using stratification factors based on the eCRF data
- repeating the main OS analysis for the PP population
- censoring OS at start of new systemic anticancer therapy including crossover therapy for patients assigned to Arm B who crossed over to selpercatinib
- censoring OS for crossover patients at start of crossover therapy for patients assigned to Arm B who crossed over to selpercatinib
- censoring OS for patients who continued study therapy beyond progression at the earliest date of study therapy after tumor progression by BICR.

Progression-free Survival 2

Progression-free survival 2 is defined as the time from randomization to disease progression on the next line of treatment or death from any cause in the absence of observed disease progression. If the patient is alive at the cutoff date for the analysis, and disease progression has not been observed, PFS2 data will be censored on the latest date of last progression-free assessment or start of the next line of treatment. [Table JZJB.10](#) defines censoring rules to be applied to the PFS2 analysis.

Progression-free survival 2 will be compared between treatment arms using a stratified logrank test, stratified by the randomization strata. The corresponding HR between treatment arms will be estimated using a stratified Cox regression model (Cox 1972), stratified by the randomization strata. Progression-free survival 2 curves, the median and PFS2 rates at various time points with 95% CI, for each treatment arm will be estimated using the Kaplan-Meier method (Kaplan and Meier 1958).

Table JZJB.10. PFS2 Censoring Scheme

Situation	Event/Censor	Date of Event or Censor
Tumor progression ^a or death on the next line of treatment	Event	Earliest date of PD or death
No tumor progression and no death on the next line of treatment	Censored	Latest date of last progression-free assessment or start of the next line of treatment
	Unless	
No baseline radiologic tumor assessment available	Censored	Date of randomization
Patient is still on study treatment	Censored	Date of last progression-free assessment
Patient discontinued the study treatment but has not started next line of treatment or		
Patient had tumor progression on study treatment but has not discontinued		
1. death	1. Event	1. Date of death
2. patient is alive	2. Censored	2. Last date the patient is known to be alive
No tumor progression prior to the start of the next line of treatment	Censored	Date of last progression-free assessment prior to the start of the next line of treatment

Abbreviations: PD = progressive disease; PFS = progression-free survival; PFS2 = progression-free survival 2; RECIST 1.1 = Response Evaluation Criteria in Solid Tumors, version 1.1.

^a Symptomatic deterioration (that is, symptomatic progression that is not radiologically confirmed per RECIST 1.1 criteria) will be considered as tumor progression.

- If there are multiple dates associated with 1 assessment, the assessment date will be set to the first date when the overall response is PD and the last date otherwise.

Adverse Events

The Medical Dictionary for Regulatory Activities (MedDRA) preferred term (PT) derived from the verbatim term will be used when reporting AEs by MedDRA terms. The MedDRA Lower Level Term (LLT) will be used in the treatment-emergent computation. Severity will be measured using the grade defined by the National Cancer Institute - Common Terminology Criteria for Adverse Events (NCI-CTCAE) version 5.0.

Treatment-emergent adverse events (TEAEs) are events that first occurred or worsened in severity after baseline and up to 30 days after core period treatment discontinuation.. Treatment-emergent adverse events will be summarized by System Organ Class (SOC) and by decreasing frequency of PT within SOC. TEAE after crossover will be defined and summarized separately in Section 8.5.

Serious adverse events (SAEs) are any AEs that result in any of the following outcomes:

- death
- initial or prolonged inpatient hospitalization
- a life-threatening experience (ie, immediate risk of dying)
- persistent or significant disability/incapacity
- congenital anomaly/birth defect
- important medical events (detailed description is contained in the protocol)

Adverse event analyses will include summaries of the following:

- AEs, including severity and possible relationship to study drug
- SAEs, including possible relationship to study drug
- AEs leading to dose adjustments
- discontinuations from study treatment due to AEs or death
- time to any toxicity grade 3 or above
- **AEs of special interest (AESI)**: Categories of AESI will be identified as the understanding of the safety of selpercatinib increases. The final list of categories will be maintained at both compound and study level and reported in the Clinical Study Report.
- **Consolidated AEs** are composite AE terms consisting of synonymous PTs to allow meaningful interpretation of the AE data. The final list of consolidated AE categories and PTs will be maintained at both compound and study level and reported in the Clinical Study Report.

Deaths

- Summary of deaths (all deaths and deaths within 30 days of last dose of study drug) and their primary cause (study disease progression, AE, other)
- Listing of TEAEs leading to death.

Laboratory Abnormalities

The severity of laboratory results will be classified according to NCI-CTCAE. Treatment-emergent changes in laboratory values will be reported for the safety population. The laboratory toxicity by worst NCI-CTCAE grade and shifts in toxicity grading from baseline to the worst postbaseline grade will be summarized.

Shift to low/high tables will include the number and percentage of patients within each baseline category (baseline value is low, normal, high, or missing) versus each postbaseline category (worst value is low, normal, high, or missing) by treatment arm.

RET Testing Results Concordance

The concordance between RET testing results based on local laboratory tests and centrally assessed results will be evaluated. Details regarding analyses involving centrally assessed RET testing results will be described in a separate diagnostics SAP.

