Medullary thyroid cancer accounts for 1% to 2% of thyroid cancers in the United States, with approximately 1000 new cases per year (SEER 2018). The majority of MTCs are sporadic, with approximately 20% to 25% hereditary due to a germline activating mutation in the *RET* gene. Most sporadic MTCs harbor activating *RET* mutations as well. National Comprehensive Cancer Network (NCCN) guidelines thus recommend germline *RET* testing for all patients diagnosed with MTC. The clinical course of MTC is highly heterogeneous, varying from indolent tumors that remain unchanged for many years to aggressive cancers associated with high mortality. Although surgery can be curative for the approximately 85% of patients who present with localized disease, approximately 50% develop recurrent disease, indicated by a rising level of serum tumor markers calcitonin (Ct) and/or carcinoembryonic antigen (CEA), which can predate the development of radiographically measurable metastases. Locally recurrent disease is treated with reoperation and/or external beam radiation therapy; however, these treatments are associated with significant morbidity and are often not curative. Metastatic MTC is incurable. Two MKIs, cabozantinib and vandetanib, have received regulatory approval for advanced MTC (irrespective of the presence or absence of a *RET* mutation), with tumor response rates of 28% and 45% and progression-free survival (PFS) improvements (over placebo) of 7.2 and 11.2 months, respectively (Wells et al. 2012, Elisei et al. 2013). However, the efficacy of these MKIs is ultimately limited by incomplete inhibition of *RET* in tumors in patients, significant toxicity from stronger inhibition of other targets (e.g., KDR/VEGFR2, EGFR, MET), and poor PK (i.e., significant drug accumulation and long half-life contributing to toxicity but not efficacy). As a result, most patients treated with these agents experience significant toxicities requiring dose interruptions, reductions (35% with vandetanib, 79% with cabozantinib), and/or treatment cessation (12% with vandetanib, 16% with cabozantinib). There are no approved systemic therapies with proven efficacy after failure of 1 prior MKI.

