As presented at World Conference on Lung Cancer (WCLC) 2018 and American Thyroid Association (ATA) 2018, with a data cutoff of July 19, 2018, the overall response rate (ORR) was 68% (95% confidence interval [CI] 51% to 83%, n = 26/38) in NSCLC, 78% (95% CI 40% to 97%, n = 7/9) in papillary thyroid cancer, 50% (n = 1/2) in pancreatic adenocarcinoma, 59% (95% CI 39% to 77%, n = 17/29) in MTC and 0% (n = 0/4) in patients without a known activating *RET* alteration in their cancers among the first 82 patients enrolled in Study LOXO-RET-17001. Updated interim results from the study are publicly available (Drilon et al. 2020; Wirth et al. 2020).

Additional information on the nonclinical pharmacology, PKs, and toxicity of selpercatinib are provided in the selpercatinib Investigator's Brochure (IB).

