9.4.3.3. Other Secondary Analyses

Overall response rate will be assessed for Arm A versus Arm B using a Cochran-Mantel-Haenszel test stratified by the randomization strata.

- ORR per RECIST 1.1 as assessed by BICR
- ORR per RECIST 1.1 per investigator assessment

The following secondary outcomes will be assessed for Arm A vs. Arm B using a logrank test stratified by the randomization strata. The corresponding HR between treatment arms will be estimated using a stratified Cox regression model (Cox 1972), stratified by the randomization strata. Point estimates with 95% CI, for each treatment arm will be estimated using the Kaplan-Meier method (Kaplan and Meier 1958):

- TFFS as assessed by investigator
- PFS as assessed by investigator
- DoR as assessed by investigator
- DoR as assessed by BICR
- PFS2 as assessed by investigator

Progression-free survival per investigator assessment is defined in the same manner as BICR PFS.

TFFS per investigator assessment is defined as the time from randomization to the first occurrence of documented radiographic disease progression per RECIST 1.1 as assessed by the investigator or unacceptable toxicity leading to treatment discontinuation as assessed by the investigator (regardless of a study drug-related AE meets protocol guidance for treatment discontinuation or not); or death (due to any cause).

Progression-free survival 2 (PFS2) is defined as the time from randomization to disease progression (radiographic or symptomatic progression as determined by the investigator) on the next line of treatment or death from any cause in the absence of observed disease progression. If the patient is alive at the cutoff for analysis, and disease progression has not been observed, PFS2 data will be censored on the latest date of last progression-free assessment or start of the next line of treatment.

Duration of response (DOR) is defined as the time from the date that measurement criteria for complete response (CR) or partial response (PR) (whichever is first recorded) are first met by the BICR or investigator assessment, as applicable, until the first date that disease is recurrent or documented disease progression is observed, per RECIST 1.1 criteria, or the date of death from any cause in the absence of documented disease progression or recurrence.

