4.2. Study Design

This is a global, multicenter, randomized (2:1), open-label, Phase 3 study comparing selpercatinib (treatment Arm A) to physicians' choice of cabozantinib or vandetanib (treatment Arm B) in patients with progressive, advanced, kinase inhibitor naïve, rearranged during transfection (RET)-mutant medullary thyroid cancer (MTC).

Patients will be randomized in a 2:1 ratio to selpercatinib or physician's choice of cabozantinib or vandetanib.

Patients will be stratified based on:

- RET mutation: M918T vs. other
- Intended treatment if randomized to control arm: cabozantinib vs. vandetanib

Approximately 250 patients will be initially enrolled in the study. A sample size re-estimation based on comparative data will be conducted at the interim efficacy analysis. The total number of patients could be increased from the initially planned 250 up to a maximum of approximately 400 depending on the results of the interim efficacy analysis. The total study duration will be capped at 6 years from the first patient visit.

Patients with histologically confirmed, unresectable, locally advanced, or metastatic MTC who have not received previous treatment with a kinase inhibitor are eligible. Patients are required to have radiologic progressive disease (PD) per Response Evaluation Criteria in Solid Tumors, version 1.1 (RECIST 1.1, Eisenhauer et al. 2009) at screening compared with an image obtained within the prior 14 months. Patients are also required to have a documented RET mutation in tumor or germline deoxyribonucleic acid (DNA) identified through molecular assays.

After confirmation of eligibility, patients will be randomly assigned in a 2:1 ratio to:

- Arm A: selpercatinib at a starting dose of 160 twice a day or
- Arm B: cabozantinib at a starting dose of 140 mg once daily, or vandetanib at a starting dose of 300 mg once daily. Patients cannot switch from cabozantinib to vandetanib or from vandetanib to cabozantinib during the study.

Treatment will continue until disease progression, unacceptable toxicity, or death. The treatment decision will be made by investigator assessment. Patients with disease progression per investigator assessment may continue treatment while awaiting blinded independent central review (BICR) confirmation of progression.

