8.1. General Considerations

Statistical analysis of this study will be the responsibility of Lilly or its designee. All tests of treatment effects will be conducted at a 2-sided alpha level of 0.05, unless otherwise stated, and all confidence intervals (CIs) will be given at a 2-sided 95% level, unless otherwise stated. Endpoints and analyses are defined for the core study period, ie study period with randomized treatment before crossover, unless otherwise specified. Statistical analysis will be performed using SAS software (SAS, version 9.1.2 or higher).

Continuous variables will be summarized using descriptive statistics (ie, number of patients, mean, median, standard deviation, minimum, and maximum). Categorical variables will be summarized by frequency and their corresponding percentage.

Any change to the data analysis methods described in the protocol will require an amendment ONLY if it changes a principal feature of the protocol. Any other change to the data analysis methods described in the protocol, and the justification for making the change, will be described in the clinical study report. Additional exploratory analyses of the data will be conducted as deemed appropriate.

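### Duration of response is tested between arms among responders only, which is not a randomized comparison; selection alone can move the hazard ratio, by an amount the documents cannot fix

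*SAP*

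**What the plan says.** SAP 8.4.2 defines the analysis set by outcome: "The DOR will be analyzed for patients who achieve a BOR of CR or PR". It then plans a between-arm test, "Duration of response will be compared between treatment arms using a stratified logrank test, stratified by the randomization strata", and an effect measure, "The corresponding HR between treatment arms will be estimated using a stratified Cox regression model (Cox 1972), stratified by the randomization strata". Kaplan–Meier curves, medians and rates with 95% CIs by arm are planned as well. Both BICR-based and investigator-based DOR are evaluated.

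Protocol 9.4.3.3 plans the same for a list that includes DoR by investigator and DoR by BICR: "The following secondary outcomes will be assessed for Arm A vs. Arm B using a logrank test stratified by the randomization strata", with a stratified Cox HR.

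On significance, SAP 8.1 says: "All tests of treatment effects will be conducted at a 2-sided alpha level of 0.05, unless otherwise stated". Nothing exempts DOR. Neither document calls the DOR comparison descriptive, notes that responders are identified after randomization, or plans a measure of response duration in all randomized patients.

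SAP 8.8 confines formal testing to PFS, then TFFS, then comparative tolerability. DOR sits under the supportive secondary endpoints.

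**The concern.** Randomization balances the arms among everyone randomized. It does not balance the subsets who go on to respond, because membership depends on how each patient reacted to the assigned drug. Stratifying by RET mutation and intended control drug adjusts for two baseline factors and leaves every other difference between the two responder groups in place.

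The direction can be awkward. An arm with a higher response rate takes in patients who would not have responded on the other drug. If response tends to go with better prognosis, the responders on the lower-rate arm are the more strongly selected group and may have longer responses for that reason alone. The DOR HR can then look unfavourable for the drug that produces more responses, or understate a real benefit. At stake is the reading of two supportive p-values and two HRs that the plan presents as treatment comparisons.

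**Working it through.** **Plan figure.** Neither document gives an event count, power or effect size for DOR, so there is nothing to reproduce for this endpoint. The trial is sized on PFS alone, and that figure does reproduce: (1.960 + 0.842)² / [(2/9) × (ln 0.5)²] = 73.5, that is 74 events.

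**Inputs from the documents**
- Allocation 2:1 and about 250 patients (SAP 4.2), so about 167 and 83.
- Selpercatinib: "59% (95% CI 39% to 77%, n = 17/29) in MTC" (Protocol 2.2.1); the synopsis also gives a confirmed rate of 56% (15/27). The trial itself requires confirmation at least 28 days later (Protocol 9.4.3.3, SAP 8.4.2).
- Cabozantinib 28% and vandetanib 45% (Protocol 2.2), for drugs approved irrespective of RET status.

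**Responder counts if those rates recurred**
- Arm A: 0.59 × 167 ≈ 99, or 0.56 × 167 ≈ 94.
- Arm B: 0.28 × 83 ≈ 23, up to 0.45 × 83 ≈ 37.

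**Arm A responders with no Arm B counterpart**, assuming everyone who would respond on control would also respond on selpercatinib
- At 59%: (0.59 − 0.28)/0.59 = 53%, down to (0.59 − 0.45)/0.59 = 24%.
- At 56%: (0.56 − 0.28)/0.56 = 50%, down to (0.56 − 0.45)/0.56 = 20%.

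**Model for the size of the shift (assumed).** Each patient has a standard normal prognosis score that lowers the log hazard of progression by 0.6 per SD, identically in both arms, so the drug has no effect on duration. Response occurs when a second normal score, correlated ρ with prognosis, exceeds the cut-off that yields the arm's response rate p. Mean prognosis among responders is then ρ × m(p), where m(p) = φ(c)/p and c is the upper-p normal quantile. To first order:

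log HR ≈ 0.6 × ρ × [m(p_B) − m(p_A)]

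with m(0.59) = 0.659, m(0.56) = 0.704, m(0.45) = 0.880 and m(0.28) = 1.202.

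| Response rate A vs B | m(p_B) − m(p_A) | ρ = 0 | ρ = 0.2 | ρ = 0.4 | ρ = 0.6 |
|---|---|---|---|---|---|
| 59% vs 28% | 0.543 | 1.00 | 1.07 | 1.14 | 1.22 |
| 59% vs 45% | 0.221 | 1.00 | 1.03 | 1.05 | 1.08 |
| 56% vs 28% | 0.498 | 1.00 | 1.06 | 1.13 | 1.20 |
| 56% vs 45% | 0.175 | 1.00 | 1.02 | 1.04 | 1.07 |

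**Simulation of the same model** (250 patients, 2:1, Cox model among responders, 1,500 trials per setting; assumed medians of 25 or 30 months and 24 to 48 months of follow-up; HRs averaged on the log scale)
- ρ = 0.4 to 0.6: mean DOR HR about 1.05 to 1.25.
- ρ = 0.2: 1.02 to 1.09.
- ρ = 0, or equal response rates: about 1.0.
- Nominally significant detriment: about 2–7% of trials, against 2.5% in that tail.
- In a run with ρ = 0.4 to 0.6 and 59% against 28–45%, total two-sided rejection was 5.0–6.0%.

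The return to 1.0 when either the rate difference or the correlation is removed shows that unequal selection produces the shift.

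**The case against.** The case against rests on size and role, and much of it stands.

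- **The p-value barely moves.** Under the model above, total rejection stays close to 5%. The main distortion is in the HR estimate.
- **The key inputs are not in the documents.** The correlation and the 0.6 per SD are assumptions, and zero correlation gives no bias. If response went with worse prognosis, the shift would reverse.
- **A wide gap in response rates is not established.** The 59% comes from 29 patients treated across a range of doses, and its CI of 39% to 77% contains 45%. Protocol 2.2 reports greater benefit from the control drugs in RET-mutant patients, so control response here may exceed 28–45%. Neither document states an expected response rate for this trial.
- **DOR carries no decision.** It is outside the alpha-controlled sequence, and the descriptive Kaplan–Meier output is already planned.

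A reader might infer something stronger: that the DOR HR will be biased against selpercatinib, or that a false detriment is likely. A harsher simulation illustrates the temptation. There, patients who would respond on either drug have a median duration of 50 months in both arms, and the additional selpercatinib responders have 20 or 30 months. The DOR HR is then 1.14 to 1.67, with a significant detriment in 5% to 24% of trials. The documents give no response durations that would support that contrast, and when the additional responders also last 50 months the HR returns to about 1.0. The certain-bias reading is therefore not supported.

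What the objection does not remove is the structural point: the plan states a test and an HR in a group selected after randomization, without saying so.

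**Conclusion.** The concern holds in a limited form. Both documents plan a between-arm test and HR for DOR among responders only, and this is not a randomized comparison. Whether it is biased, and by how much, depends on whether response rates differ and whether response tracks prognosis. Under the assumed model the mean HR with no true effect lies between about 1.0 and 1.25.

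It would be wrong to infer that the efficacy conclusion is at risk. PFS and TFFS are compared in all randomized patients, and ORR uses all randomized patients as its denominator. This is an inexpensive improvement to a supportive analysis.

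**What to change.** In SAP 8.4.2 and Protocol 9.4.3.3 together, remove the logrank test and HR for DOR by BICR and by investigator. Keep the planned Kaplan–Meier curves, medians and rates with 95% CIs by arm, described as descriptive summaries among responders. Changing only the SAP would leave the two documents in conflict.

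If a between-arm comparison is wanted, prespecify one in all randomized patients, such as mean time in response up to a fixed time with non-responders counted as zero. If the sponsor prefers to keep the HRs, the minimum is a sentence stating that they are non-randomized and not for inference.

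The cost is two supportive p-values and two HRs. No sample size, power or alpha figure changes. Protocol 9.4.1 requires an amendment only when a principal feature changes, so this edit could travel with the next amendment or be recorded in the clinical study report.
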